14.1.2. Model of End Stage Liver Disease Score

The MELD scoring system is used to assess the severity of chronic liver disease. The MELD score is useful in assessing patients with significant decompensation, and the MELD score is now used by the United Network for Organ Sharing in the US and Eurotransplants to manage the organ allocation for liver transplantation. The threshold for placement on an organ transplantation queue varies between regions across the globe.

An increasing MELD score is associated with increased severity of hepatic dysfunction and increased 3-month mortality risk. The MELD score is derived from the patient's serum total bilirubin, serum creatinine, and INR, as appropriate, to predict survival ([Kamath 2007](#)). MELD score will be calculated and reported for visits where these parameters are measured (see [Table 1](#)).

14.1.3. Changes in Liver Biochemistry and Hepatobiliary Damage

ALP, ALT, AST, GGT, total and direct bilirubin, INR, creatinine, albumin, platelets will be measured according to the frequency listed in [Table 1](#).

14.2. Additional Assessments

14.2.1. Noninvasive Measurements of Liver Stiffness and Fibrosis

The ELF test assesses: HA, P3NP, and TIMP-1. Samples will be assessed in patients according to the schedules presented in [Table 1](#).

The Fibroscan[®] TE device (Echosens, Paris, France) will be used at all study sites that have the equipment to collect hepatic stiffness measurements. These study sites must have the staff trained in the use and data interpretation of the device. This is a validated and non-invasive radiological technique used to assess hepatic fibrosis which will be conducted according to the schedule presented in [Table 1](#).

14.2.2. Markers of FXR activation

Blood samples will be collected in all patients to measure C4, FGF-19, and bile acids. The results of these analyses will be used to assess the PK/PD response of OCA. Blood samples will be assessed in patients according to the schedule presented in [Table 1](#).

14.2.3. Clinical Outcome Events

Clinical outcome events will be evaluated by an Adjudication Committee (described in [Section 15.9](#)) to confirm if they meet the criteria to be considered Clinical Outcome Events.

15. STATISTICAL METHODS AND ANALYSES

Individual patient data obtained from electronic case report forms (eCRFs), central laboratories, external sources, and any derived data will be presented in data listings by patient. All data listings that contain an evaluation date will contain a relative study day. Pre-treatment and on treatment study days are numbered relative to the day of the first dose of investigational product which is designated as Day 1.

All output will be incorporated into Microsoft Word rich text format (.rtf) files, sorted and labeled according to the International Conference on Harmonisation (ICH) recommendations, and formatted to the appropriate page size(s).

Tabulations will be produced for appropriate demographic, Baseline, efficacy, and safety parameters.

For categorical variables, summary tabulations of the number and percentage of patients within each category (with a category for missing data) of the parameter will be presented. Percentage calculations will be based on non-missing data, unless otherwise specified. Percentages are rounded to 1 decimal place, unless otherwise specified.

For continuous variables, the number of patients, mean, standard deviation (SD), standard error of the mean (SEM), median, minimum, and maximum values will be presented. The precision of summary statistics, unless otherwise specified will be as follows: mean and median to 1 more decimal place than the raw data, and SD and SEM to 2 decimal places more than the raw data. In general, the decimal places should not exceed 3 decimal places unless appropriate. Confidence intervals (CIs) will be provided and will be rounded to 1 decimal place, unless otherwise specified.

Time-to-event data will be summarized using Kaplan-Meier (KM) methodology using 25th, 50th (median), and 75th percentiles with associated 2-sided 95% CIs, as well as percentage of censored observations.

There will be no formal hypothesis testing in this study. However, summary statistics for each treatment group will be presented, as well as 95% CIs for the difference between the treatment groups.

15.1. Analysis Populations

The following patient populations will be evaluated and used for presentation and analysis of the data:

- The Intent-to-Treat (ITT) Population will include all randomized patients who receive any amount of investigational product (OCA or placebo). The ITT Population will be the primary population used for summarizing efficacy assessments.
- The Safety Population will include all patients who received at least one dose of investigational product (placebo or OCA). The Safety Population will be the primary population used for safety analyses.
- The PK population will include all patients receiving OCA who have adequate concentration-time profiles to characterize OCA and its conjugates and must not have any major protocol deviations that potentially affect exposure levels.

15.2. Determination of Sample Size

To reasonably characterize the PK of OCA in patients with hepatic impairment, a simulation-based approach estimated a requirement of approximately 20 patients in the OCA treatment group assuming a 15% discontinuation rate. A total of 30 patients is adequate with 10 patients on placebo to be included as a comparator and 20 patients on OCA. An additional

20 patients will be enrolled to support safety and efficacy evaluations. Therefore, approximately 50 patients (including at least 20% of patients with CP-C) will be randomized in a 1:1 ratio to 1 of the 2 treatment groups: Placebo and OCA.

15.3. Pharmacokinetic Analyses

The PK Population will be used for analysis of PK parameters, which include plasma OCA (parent) and its conjugates (glyco-OCA and tauro-OCA), total OCA, metabolite OCA glucuronide, and potentially other conjugates or metabolites not yet identified.

PK analysis will be based on the PK population. Values will be calculated using non-compartmental methods. The values will be summarized by active treatment group using descriptive statistics. Full details regarding the planned analyses, methods, and outputs for the study will be detailed in the statistical analysis plan (SAP).

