5.4.2. Rationale for Obeticholic Acid Dose and Duration

Simulations using a physiologic PK model predicted changes in systemic and liver OCA concentrations associated with changes in the severity of hepatic impairment (CP Score). Model simulations predicted that for mild (Child-Pugh A [CP-A]), moderate (Child-Pugh B [CP-B]), and severe (Child-Pugh C [CP-C]) hepatic impairment, total OCA plasma concentrations increase 1.4-, 8.0-, and 13-fold relative to patients with normal hepatic function, whereas total OCA liver concentrations increase 1.1-, 1.5-, and 1.7-fold, respectively. Because the liver is the primary site of action for the safety and efficacy of OCA, it is important to account for the differences in systemic and liver exposure when assessing effective doses. It is also important to note that while hepatically impaired (CP-B and C) patients treated with OCA in Phase 1 and 2 studies experienced plasma OCA exposures >10-fold higher than those in healthy patients, no apparent impact on the overall safety profile was observed, consistent with only a modest

increase in liver exposure of OCA associated with hepatic impairment. Together, the results from these analyses suggest that the doses of OCA administered to patients with moderate or severe hepatic impairment should be modestly lower than those for patients with normal hepatic function to achieve similar hepatic exposure.

Therefore, the current FDA-approved prescribing information for OCA includes a modified dosing regimen in patients with moderate and severe hepatic impairment that is designed to achieve liver exposures in these patients that would be similar to non-hepatically impaired patients through initiation at a lower dose (5 mg OCA once-weekly) followed by gradual up-titration ([Section 7.3](#)).

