6.1. Primary Objectives

- To evaluate the PK of OCA and its conjugates, glyco-OCA and tauro-OCA, and OCA metabolite glucuronide compared with placebo
- To evaluate the safety and tolerability of OCA treatment compared with placebo

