7.3. Planned Dosing Regimen

All patients will initiate investigational product once weekly with OCA 5 mg or matching placebo (Table 2). Titration may be considered as early as the Week 12 Visit. Following visit procedures at Week 12, if the investigational product is tolerated and laboratory assessments do not indicate a safety concern, the patient may up-titrate to OCA 5 mg twice weekly and may start the higher dose regimen no earlier than 2 days after they took their last dose. Dosing will then occur at least 3 days apart. Every 6 weeks thereafter, based on tolerability assessments, patients can be considered for further up titration as described below (Table 2). At each titration visit, the patient may start the higher dose regimen no earlier than 2 days after the prior dose.

Patients may titrate to a maximum dose of OCA 10 mg twice weekly at least 3 days apart.

Table 2: Planned OCA or Matching Placebo Dosing Regimen

	Child-Pugh B and Child-Pugh C (Moderate and Severe Hepatic Impairment)	
	Treatment Group	
	OCA	Placebo
Starting Dose (Day 1)	5 mg once weekly	matching placebo once weekly
Titration 1 ^a	5 mg twice weekly ^b	matching placebo twice weekly ^b
Titration 2 ^a	10 mg twice weekly ^b	matching placebo twice weekly ^b

^a Planned titration regimen is shown; however, the titration of dose and/or frequency is dependent on patient tolerability.

^b Dosing per the twice weekly schedule must be at least 3 days apart.

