9. TREATMENT OF PATIENTS

9.1. Investigational Product Treatment Regimen

The term investigational product refers to either OCA (provided as part of this clinical study) or placebo.

Two treatment groups will be evaluated: OCA and placebo. Investigational product will be administered orally. Each dose will be made up of 1 tablet (ie, one OCA 5 mg tablet or one OCA 10 mg tablet, or matching placebo).

Investigational product will be taken orally with water for the duration of the study. Patients will be instructed to begin dosing on Day 1 and are to take investigational product at approximately the same time on dosing days. Patients must be instructed to swallow the tablet whole; they must not chew, divide, or crush the tablet.

At each study visit where the dose of investigational product is administered at the site, all assessments, except for the post-dose collection of blood samples for the PK assessment, must be completed before administration of investigational product.

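### The primary PK objective asks for a placebo comparison that the PK population rules out, and the only PK grouping stated combines dose regimens and Child-Pugh classes

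*Protocol*

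**What the plan says.** Protocol Section 6.1 states the first primary objective as: "To evaluate the PK of OCA and its conjugates, glyco-OCA and tauro-OCA, and OCA metabolite glucuronide compared with placebo". The synopsis (Section 2) says the same.

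Section 15.1 defines the PK set: "The PK population will include all patients receiving OCA who have adequate concentration-time profiles to characterize OCA and its conjugates". These patients also "must not have any major protocol deviations that potentially affect exposure levels".

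Section 15.3 bases the PK analysis on that population, uses non-compartmental methods, and then states: "The values will be summarized by active treatment group using descriptive statistics". Its next sentence leaves the full analyses, methods and outputs to the SAP.

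Section 9.1 shows that there is only one active group: "Two treatment groups will be evaluated: OCA and placebo". Within it the regimen can change. Section 7.3 begins: "All patients will initiate investigational product once weekly with OCA 5 mg or matching placebo". After the Week 12 visit procedures a patient may move to 5 mg twice weekly, and later to at most 10 mg twice weekly. Steps are at least 6 weeks apart and depend on tolerability (Sections 7.3 and 7.5).

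On Child-Pugh class (mild, moderate and severe impairment in that order), Section 5.4.2 reports model predictions that "total OCA plasma concentrations increase 1.4-, 8.0-, and 13-fold relative to patients with normal hepatic function". Randomisation is stratified by class B or C (Section 9.4.1). Serial PK profiles are planned at Weeks 12, 18, 24, 30 and 48 (Section 12.1).

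**The concern.** The objective names a contrast that cannot be estimated. Placebo patients have no OCA exposure to compare, and the analysis population leaves them out. An objective sits in the protocol, so the SAP cannot repair it.

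Section 5.4.1 says the study is meant to characterise PK in moderate to severe impairment. The one grouping that Section 15.3 names separates neither severity nor dose. Titration follows tolerability, so the regimen a patient is on at a given visit is not random. Regimen and class therefore need to be separated together. For example, if class C patients stayed on 5 mg per week while class B patients moved to 10 mg per week, the expected C:B exposure ratio under dose proportionality would be 1.625/2 = 0.81, which reverses the predicted direction. The efficacy models in Sections 15.5 and 15.6 carry the stratification factor; the PK summary as written does not.

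The PK population rule is also written about patients, although each patient is to give five serial profiles. Read literally, one major deviation affecting exposure at Week 48 discards sound profiles from Weeks 12 to 30.

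**Working it through.** **1. The plan's own numbers.** Section 15.2: 20 OCA + 10 placebo + 20 additional = 50, which adds up. The figure of 20 for PK comes from a simulation whose inputs are not given, so it can be neither confirmed nor refuted. It implies 20 × 0.85 = 17 patients after 15% discontinuation. Randomising 50 patients 1:1 gives 25 on OCA, or 25 × 0.85 = 21.25 after the same loss. At the 20% minimum for class C, 50 × 0.20 / 2 = 5 class C patients receive OCA (5 × 0.85 = 4.25 after loss).

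**2. Objective against population.** Objective: PK compared with placebo (Sections 2 and 6.1). Population: OCA recipients only (Section 15.1). Summary: active group only (Section 15.3). These cannot all hold.

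**3. Regimens present at each serial profile, by plan.** The first step follows the Week 12 procedures, the next comes at least 6 weeks later, and a new regimen starts no sooner than 2 days after the prior dose. The Week 18 profile uses the bottle the patient brings (Section 9.7.10).
- Week 12: 5 mg once weekly only.
- Week 18: 5 mg once or twice weekly.
- Weeks 24, 30 and 48: all three regimens possible.

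**4. Expected span within the group**, assuming dose-proportional exposure. Class ratio: 13/8.0 = 1.625. Values are relative to class B on 5 mg once weekly.

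| Scale | Class | 5 mg once weekly | 5 mg twice weekly | 10 mg twice weekly |
|---|---|---|---|---|
| Weekly dose | B | 1.0 | 2.0 | 4.0 |
| Weekly dose | C | 1.63 | 3.25 | 6.5 |
| Administered dose | B | 1.0 | 1.0 | 2.0 |
| Administered dose | C | 1.63 | 1.63 | 3.25 |

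**5. Effect on a pooled summary.** Assumptions, none from the protocol: within-cell CV 60%, one third of patients on each regimen (possible only from Week 24), and an 80/20 split of class B to C. Log-scale variances:
- Within cell: ln(1 + 0.60²) = 0.307.
- Class: 0.8 × 0.2 × (ln 1.625)² = 0.038.
- Dose, administered scale (5, 5, 10 mg): (1/3)(2/3)(ln 2)² = 0.107.
- Dose, weekly scale (5, 10, 20 mg): (2/3)(ln 2)² = 0.320.

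Pooled geometric CV = √(exp(total) − 1); CI width ratio at the same n = √(total/within).
- Administered scale: total 0.452, CV about 76%, ratio √(0.452/0.307) = 1.21.
- Weekly scale: total about 0.666, CV about 97%, ratio √(0.666/0.307) = 1.47.

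For within-cell CVs of 30% / 50% / 80%, the pooled CV is 51% / 67% / 95% on the administered scale and 75% / 89% / 116% on the weekly scale. At Week 12, where only class is mixed, it is 36% / 55% / 84%.

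**6. Patient-level exclusion.** If each of five profiles independently carried a major exposure-affecting deviation with probability p, the share of patients lost would be 1 − (1 − p)⁵. Of 25 OCA patients, p = 5% loses 23% and leaves 19.3; 10% loses 41% and leaves 14.8; 15% loses 56% and leaves 11.1. The benchmark from step 1 is 17. Both p and independence are assumptions, and clustering of deviations within patients would reduce the loss.

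**The case against.** The strongest reply is that Section 15.3 hands the details to the SAP in its next sentence. Tables by visit, regimen and class, and dose normalisation, are ordinary SAP content. The protocol nowhere says that regimens, visits or classes go into one column. That stands: pooling is what the sentence permits, not what it declares. It does not rescue the objective, which the protocol itself contradicts.

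Four stronger readings are tempting, and the protocol does not support them:
- A reader might infer that the trial's main question goes unanswered. Week 12 is a common-regimen profile by plan, class is a stratification factor and five serial profiles are scheduled, so the needed data are collected. Safety against placebo, the other primary objective, is unaffected.
- A reader might infer that three regimens mix from Week 18. By plan only the two 5 mg regimens can be present then.
- A reader might take 6.5-fold as the span fixed by the design. Profiles follow a single 5 mg or 10 mg tablet over 24 hours, and on that scale the span is 3.25-fold. Accumulation could push it higher, so both ends should be shown.
- A reader might infer that the population rule will take the PK set below its planned size. The rule covers major deviations only, no rate is given, at 5% the remaining 19.3 exceeds 17, and 25 patients are randomised to OCA against the 20 sought.

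The study is descriptive, with no formal testing (Section 15). A modelled class C to B ratio is therefore not something that the objectives require.

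**Conclusion.** The inconsistency in the primary PK objective is certain and needs correcting, although no planned PK result depends on the placebo wording. The grouping in Section 15.3 is too coarse as stated for what the study sets out to learn. From Week 24, one active-group column could span 3.25- to 6.5-fold in expected exposure and widen the log-scale interval 1.21 to 1.47 times. Those figures rest on dose proportionality, the protocol's own 8.0- and 13-fold predictions, and the assumed CV, regimen mix and class split. The SAP may already separate these cells. The patient-level exclusion rule is a real weakness in wording, but the size of its effect cannot be known from the protocol.

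**What to change.** - **Synopsis and Section 6.1:** delete *compared with placebo* from the PK objective and state that PK is characterised by Child-Pugh class and dose regimen. Leave the safety objective as it is.
- **Section 15.3:** state that PK parameters are summarised by visit, regimen at sampling and Child-Pugh class, with dose-normalised total OCA. If the SAP already does this, say so here.
- **Section 15.1:** exclude the affected profile, not the patient.
- **Optional:** a log-scale mixed model over all profiles giving a class C to B ratio.

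The cost is a few sentences and modest PK programming; design, sample size and dosing do not change. The drawback is small cells. With about 5 class C patients on OCA and a within-cell CV of 30% / 50% / 80%, the 95% CI of a geometric mean is the estimate multiplied and divided by 1.44 / 1.80 / 2.39, against 1.14 / 1.24 / 1.38 with 21 patients. Splitting class C further by regimen makes this worse, so the cell sizes should be shown plainly.

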15.4. Safety Analyses

Safety analyses will be conducted using the Safety population. Safety data, including AEs, AEs of special interest including pruritus and hepatic safety, vital signs, ECG, and clinical laboratory results will be summarized by treatment group using the Safety Population.

The incidence of TEAEs and SAEs will be tabulated by system organ class (SOC) and preferred term (PT) for each treatment group, and similarly by severity and relationship to treatment.

Laboratory parameters, physical examinations including vital signs, and ECGs will be summarized by treatment group using descriptive statistics at Baseline and at each scheduled post-Baseline visit. The absolute change from baseline will also be summarized.

No inferential comparison with formal statistical hypothesis testing will be performed for safety endpoints.

15.4.1. Adverse Events

AEs will be coded using Medical Dictionary for Regulatory Activities (MedDRA). Summary tables of TEAEs will be provided.

Each AE summary will be displayed by treatment group. Summaries that are displayed by SOC and PT will be ordered by descending order of incidence of SOC and PT within each system organ class. Summaries of the following types will be presented:

- Overall summary of TEAEs.
- Patient incidence of TEAEs and the total number of entries by MedDRA SOC and PT. This summary will be repeated for all subgroups.
- Patient incidence of TEAEs by MedDRA SOC, PT, and highest severity. At each level of patient summarization, a patient is classified according to the highest severity if the patient reported 1 or more events. AEs with missing severity will be considered severe for this summary.
- Patient incidence of TEAEs by MedDRA SOC, PT, and closest relationship to investigational product (Related/Not Related). Related AEs are those with relationships reported as “Definite,” “Probable,” or “Possible,” and unrelated AEs are

those with relationships reported as “Unlikely” or “Not Related.” At each level of patient summarization, a patient is classified according to the closest relationship if the patient reported 1 or more events. AEs with a missing relationship will be considered related for this summary.

- Patient incidence of serious TEAEs and the total number of entries by MedDRA SOC and PT.
- Patient incidence of TEAEs leading to investigational product withdrawal or study discontinuation by MedDRA SOC and PT. This is a subset of the AEs where Action Taken with Study Treatment is checked as “Drug Withdrawn” or where “Patient Discontinued from Study” is checked.

The following listings will be presented by treatment group and patient:

- All adverse events.
- Serious adverse events (This is a subset of the AEs where serious is marked as “Yes”).
- Severe adverse events (This is a subset of AEs where severity is marked as “Severe”).
- Related adverse events (This is a subset of the AEs where relationship marked as “Definite,” “Probable,” or “Possible”).
- Adverse events leading to Study Drug Withdrawal or Study Discontinuation (This is a subset of the AEs where Action Taken with Study Treatment is checked as “Drug Withdrawn” or where “Patient Discontinued from Study” is checked).
- Adverse events leading to death (This is a subset of the AEs where the corresponding AE number is specified on the Death eCRF).

Adverse events of special interest as defined in [Section 13.1.1.4](#) will be summarized for each treatment group.

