5.4.4. Rationale for Control Group

The use of a randomized placebo control group added to established standard of care provides the best scientific evidence of efficacy and safety. The use of a placebo control provides a concurrent comparator group, accounting for not only a placebo effect but continued standard of care. The use of a placebo control is critical to assess the safety and tolerability of OCA but also as a comparator for the high rate of clinical events which are expected in this advanced population.

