7.1.3. Study Duration

Patients will receive double-blind treatment for at least 48 weeks. Patients who have completed their 48-week, double-blind treatment period will continue double-blind treatment until all randomized patients have completed their 48-week treatment period and the database for that period is locked (approximately 3 years). An open-label extension study in which all patients receive OCA will be considered following review of blinded safety and PK data.

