13.1.1.4. Adverse Events of Special Interest

The following decompensation events are adverse events of special interest; a subset of these are also captured as additional efficacy assessments (see [Section 14.2.3](#)).

- Variceal bleeding or recurrent variceal bleeding documented by endoscopy OR patient presenting with anemia or melena (hemoglobin drop ≥ 2 g/dL) and found to

have varices documented by endoscopy, irrespective of hospitalization or requirement of blood transfusion.

- Gastrointestinal bleeding as a result of gastric or duodenal varices verified by endoscopy
- Hepatic encephalopathy, Grade ≥ 2
- New onset ascites requiring treatment
- Worsening of ascites (requiring increase in drug therapy or requirement of surgical procedure such as paracentesis or shunt placement)
- Refractory ascites -unresponsive to medications, and patient is not a candidate for TIPS or shunt and requires large volume paracentesis
- Hyponatremia ($\text{Na} \leq 125$ mEq/L) secondary to ascites
- Spontaneous bacterial peritonitis (confirmed by diagnostic paracentesis- by cell count/chemistry)
- Hepatorenal syndrome Type 1 and Type 2 and Acute Kidney Injury (AKI)
- Liver failure defined as worsening of liver synthetic function that is persistently worse relative to baseline and/or progressive over time:
 - Hepato-pulmonary syndrome
 - Porto-pulmonary syndrome
 - Liver Transplant
 - Increase in MELD scores by 3 points relative to baseline, persistent over time and unrelated to vitamin K deficiency related increase in INR
 - Any liver related event that requires hospitalization and treatment

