15.4.4. Adverse Events of Special Interest

Pruritus: Treatment-emergent pruritus, defined as any PT including “Prur,” will be summarized separately by the MedDRA SOC, treatment group, and PT as a subset of all TEAEs. This summary will be repeated for patients with “new or worsened” pruritus events, as defined as follows:

- Mild, moderate, or severe treatment-emergent pruritus events in patients with no pruritus at Baseline, or
- Worsening of the severity of the Baseline condition in patients with pruritus at Baseline.

Baseline pruritus is defined as the Investigator’s rating of severity as collected on the PBC Disease History eCRF. Patients whose Baseline severity is severe will be counted as worsening if an AE of pruritus with severe is recorded.

An analysis of treatment-emergent pruritus event days per patient years on study will be performed. The days at each severity grade, including the total days of event, the total patient years on study, and the event days per patient year on study at each severity grade, including the total, will be summarized. Each individual patient year on study will be derived as the last known date during the study minus the first dose date plus 1 divided by 365.25 days/year.

In order to explore the relationship between pruritus and the investigational product, the following time-to-event analyses will be performed:

- Time to first onset of treatment-emergent pruritus
 - The time to the start of the first episode will be calculated by date of onset of first episode – date of first dose of investigational product + 1.
 - Patients who never reported an AE of pruritus will be censored at the date of last contact.
- Time to onset of the first moderate or severe treatment-emergent pruritus
 - The time to the start of the first moderate or severe pruritus will be calculated by date of onset of the first moderate or severe pruritus – date of first dose of investigational product +1.

- Patients who never reported a moderate or severe AE of pruritus will be censored at the date of completion or discontinuation.
- Time to onset of the first severe treatment-emergent pruritus
 - The time to the start of the first severe pruritus will be calculated by date of onset of the first severe pruritus – date of first dose of investigational product +1.
 - Patients who never reported a severe AE of pruritus will be censored at the date of completion or discontinuation.

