15.6. Additional Efficacy Analyses

Analyses of changes in liver stiffness (TE) and liver fibrosis (ELF [HA, P3NP, and TIMP-1]) will be summarized and analyzed using the same methodology specified for the key secondary analyses of change in bilirubin.

The following clinical endpoints will be captured in the study:

- Time to death (all cause)
- Time to liver-related death
- Time to liver transplant
- MELD score ≥ 15 (for patients with MELD ≤ 12 at baseline)
- Hospitalization (as defined by a stay of 24 hours or greater) for new onset or recurrence of:
 - Time to variceal bleed
 - Time to hepatic encephalopathy (as defined by a West Haven score of ≥ 2)
 - Time to spontaneous bacterial peritonitis (confirmed by diagnostic paracentesis)
- Time to uncontrolled ascites (diuretic resistant ascites requiring therapeutic paracentesis at a frequency of at least twice in a month).

The incidence and time to first occurrence of any above listed clinical events will be summarized by treatment group using the log rank test stratified by the randomization stratification factor. KM estimates of the distribution of the time-to-event will be tabulated and graphed by treatment group. The tabulation will include the KM methodology using 25th, 50th (median), and 75th percentiles with associated 2-sided 95% confidence intervals (CIs), as well as percentage of censored observations. The number and percent of patients censored and with events will be presented. The hazard ratio and 2-sided 95% CI will be estimated based on a Cox regression model stratified by randomization strata.

In addition, the incidence and time to each of the above clinical events, and the incidence and time to occurrence of hepatocellular carcinoma (HCC) will be summarized by treatment group using the same methods as defined above.

Full details regarding additional efficacy analyses will be detailed in the SAP.

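### The TEAE and serious-TEAE tables use crude patient incidence with no stated period or patient-time denominator, so unequal loss from the study would lower one arm's figures at the same true rate

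*Protocol*

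**What the plan says.** Section 6.1 makes safety and tolerability against placebo a primary objective. Section 15.4.1 lists the tables one by one. The main one is "Patient incidence of TEAEs and the total number of entries by MedDRA SOC and PT"; the serious-event table is "Patient incidence of serious TEAEs and the total number of entries by MedDRA SOC and PT". The tables by severity, by relationship and for events leading to withdrawal also use patient incidence. None names a reporting period or a time denominator.

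The observation window is wide:
- Under Section 13.1.1.3 an event counts as treatment-emergent from first dose, with no closing date.
- Under Section 13.1.4.1 adverse events are collected until the patient's participation ends.
- Under Section 7.1.3 patients are treated double-blind for at least 48 weeks and continue "until all randomized patients have completed their 48-week treatment period and the database for that period is locked (approximately 3 years").

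Follow-up is taken into account elsewhere. Section 15.4.4 states: "An analysis of treatment-emergent pruritus event days per patient years on study will be performed". It adds Kaplan-Meier times to first, first moderate-or-severe and first severe pruritus, and repeats the whole set for fatigue.

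For the hepatic events of special interest in Section 13.1.1.4, Section 15.4.1 says only that they "will be summarized for each treatment group". Section 13.1.1.4 notes that "a subset of these are also captured as additional efficacy assessments". For the clinical events in Section 15.6, "KM estimates of the distribution of the time-to-event will be tabulated and graphed by treatment group", with a stratified log-rank test and a stratified Cox model.

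**The concern.** The percentage of patients with an event depends on the event rate and on how long patients are watched. When observation time differs between arms, the percentage differs even if the rate does not. The protocol expects substantial loss of observation time: Section 5.4.4 justifies the placebo group as a "comparator for the high rate of clinical events which are expected in this advanced population". Death, full withdrawal of consent and loss to follow-up all end adverse event collection.

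At stake is the descriptive safety comparison. Section 15.4 plans no formal safety tests, so readers will set the two percentage columns side by side. An arm that loses more patients would then look better on its remaining adverse events.

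**Working it through.** The protocol gives no expected event percentage, so there is no figure to reproduce. The check asks how far crude incidence departs from equality when the true rate is the same in both arms.

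**Inputs from the protocol**
- Minimum follow-up: 48 weeks, a = 336/365.25 = 0.920 year (Section 7.1.3).
- Longest follow-up: about 3 years, b = 3 (Section 7.1.3).
- Arm size: about 50 patients randomised 1:1, so about 25 per arm (Section 15.2).
- Discontinuation: 15%, stated for the OCA group only (Section 15.2).

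**Assumptions**
- Constant first-event rate λ, the same in both arms.
- Constant rate of loss from the study, g = −ln(1 − p)/a, where p is the proportion lost by Week 48. One arm takes p = 15%, borrowed from Section 15.2; the other takes 30%. The protocol gives no loss figure for placebo.
- Planned follow-up T uniform between a and b.

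**Formula.** With h = λ + g, the expected crude incidence is

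(λ/h) × {1 − [exp(−ha) − exp(−hb)] / [h(b − a)]}.

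**Numbers for λ = 0.3 per year**
- 15% lost: g = 0.1625/0.920 = 0.177, h = 0.477. Incidence = 0.629 × [1 − (0.645 − 0.239)/0.992] = 37.2%, or 9.3 of 25.
- 30% lost: g = 0.3567/0.920 = 0.388, h = 0.688. Incidence = 0.436 × [1 − (0.531 − 0.127)/1.431] = 31.3%, or 7.8 of 25.
- Ratio 31.3/37.2 = 0.84, a difference of 5.9 points or 1.5 patients.

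Mean time at risk is incidence divided by λ: 0.372/0.3 = 1.24 years against 0.313/0.3 = 1.04 years. Dividing events by time at risk gives 0.30 per year in both arms, a rate ratio of 1.00.

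**Range: ratio of crude incidences, same true rate in both arms**

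| Events per year | Loss 15% / 15% | 15% / 30% | 5% / 25% | 15% / 40% |
|---|---|---|---|---|
| 0.1 | 1.000 | 0.828 | 0.785 | 0.721 |
| 0.3 | 1.000 | 0.842 | 0.803 | 0.743 |
| 0.6 | 1.000 | 0.861 | 0.826 | 0.772 |
| 1.0 | 1.000 | 0.882 | 0.853 | 0.805 |
| 2.0 | 1.000 | 0.918 | 0.898 | 0.862 |

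**Cut at Week 48.** For λ = 0.3 and loss of 15% against 30%, incidence is 22.3% against 20.5%, about half a patient in 25. Over all the unequal-loss scenarios the ratio is 0.85 to 0.94. The bias shrinks but remains.

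**Hepatic events of special interest.** Setting Section 13.1.1.4 beside Section 15.6:
- Covered by Kaplan-Meier and Cox in 15.6: liver transplant; hospitalised variceal bleeding, encephalopathy and spontaneous bacterial peritonitis; uncontrolled ascites as 15.6 defines it.
- Not covered: new-onset ascites needing treatment, worsening ascites, hyponatremia, hepatorenal syndrome and acute kidney injury, hepatopulmonary and portopulmonary syndrome, a persistent 3-point MELD rise, and variceal bleeding without hospitalisation.

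**The case against.** The strongest objection is that this belongs in the SAP. Section 15.4.1 does not say its list is complete, and exposure-adjusted columns and a reporting period are common SAP content. That limits the point: nothing in the protocol forbids the addition. It does not remove it, because the protocol names the statistic table by table and specifies patient-years for two symptoms but not for TEAEs or SAEs.

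Second, the tables may be meant for the 48-week period only. Section 7.1.3 ties a database lock to that period, and Section 15.5 equates Week 48 with the end of the study. No section says which period the adverse event tables cover. This stands, and it is why the period needs stating.

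Third, the bias needs unequal loss from the study, for which the protocol offers no evidence. Stopping study drug is not such a loss: Section 8.4 expects those patients to stay in the study, where collection continues. This stands too.

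Fourth, the model treats loss as event-free. In practice a fatal event or an event leading to withdrawal is itself counted, and deaths have their own listing and time-to-event analysis. The model therefore applies to a patient's other events. A reader might infer that an arm with more deaths would look safer overall; the documents do not support that.

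Finally, rates per patient-year assume a roughly constant hazard and treat death as non-informative censoring. They supplement the crude tables and do not replace them.

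**Conclusion.** The point holds as a gap worth closing. Section 15.4.1 makes crude incidence the only named measure for TEAEs and SAEs, without a period or time denominator, while follow-up may differ about threefold between patients. Under the assumed unequal losses the crude ratio falls to between 0.72 and 0.92 at identical true rates, and to 0.84 in the central case. Event rates, per-arm loss and uniform follow-up are all assumptions. The central bias of 5.9 points is smaller than the sampling error with 25 per arm (standard error √(0.372 × 0.628/25 + 0.313 × 0.687/25) = 0.134), but it is systematic and avoidable.

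Three stronger readings are not supported:
- That hepatic events of special interest are fixed as crude percentages. The protocol says only that they are summarised, and those that are also clinical outcome events have Kaplan-Meier and Cox analyses. The gap concerns the others.
- That variable follow-up is enough to cause bias. With equal loss the ratio is 1.00, because 1:1 randomisation balances staggered entry.
- That the distortion is 10 points or more. A gap of about 11 points (58.0% against 47.4%, at 0.4 events per year and annual loss of 15% against 30%) arises only if every patient is given 3 years of follow-up, which staggered entry rules out.

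**What to change.** In Section 15.4.1:
1. State the analysis period, and present the crude TEAE and SAE tables twice: for the 48-week period common to all patients, and for all double-blind follow-up.
2. Add, by arm, first-event rates per 100 patient-years at risk for TEAEs, SAEs and each event in Section 13.1.1.4. Time at risk runs from first dose to first event or last known date.
3. Give 95% confidence intervals for the rate difference only for overall SAEs and the Section 13.1.1.4 events. With about 25 patients per arm, an interval for every preferred term would add many uninformative rows.

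Both parts are needed: the Week 48 cut reduces the bias without removing it, and the rates address the rest. The dates are already collected, and Section 15.4.4 already defines patient-years on study for pruritus and fatigue. Trial conduct does not change. The cost is longer safety tables.
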